7. STATISTICAL ANALYSIS

Statistical analysis will be performed by the research team at Radboud university medical center. First we describe the general outline of statistical analyses, then we discuss specific statistical procedures for the primary and secondary objectives separately, if appropriate.

In general, continuous variables will be described using standard summary statistics (e.g. mean, medians and corresponding 95% confidence interval (CI),); categorical variables will be described using frequencies and percentages with their 95% CIs. Group differences will be determined using analysis of variance (ANOVA) or Student's t-test for continuous variables and Fisher's exact test for categorical variables (Fisher-Freeman-Halton exact test for variables with more than two categories). Non-parametric tests will be used for results with non-normal distributions. Two-sided p-values smaller than 0.05 will be considered statistically significant. Because of the explorative character of this study no correction for multiple testing will be applied.

The following parameters will be categorized when appropriate:

- Bleeding score (ISTH-BAT): ≥ 5 abnormal for women, ≥ 3 abnormal for men
- Clinical bleeding severity [19]:
 - Asymptomatic: no documented bleeding episodes
 - Grade I bleeding: bleeding that occurred after trauma or drug ingestion (antiplatelet or anticoagulation therapy)
 - Grade II bleeding: spontaneous minor bleeding (bruising, ecchymoses, minor wounds, oral cavity bleeding, epistaxis and menorrhagia)
 - Grade III bleeding: spontaneous major bleeding (intramuscular haematomas requiring hospitalizations, haemarthrosis, bleeding of the central nervous system, the umbilical cord or the gastrointestinal tract)

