5. STUDY POPULATION

5.1. Population (base)

Based on the prevalence in the general population of 1:500,000 to 1 per 2 million persons [1, 2], and a total population of 17 million, there should be 129 to 145 individuals with a homozygous rare bleeding disorder in the Netherlands. This could be higher taking into account the possible influences of high-risk populations such as Ashkenazi or Iraqi Jews with high FXI deficiency rates. To date, 337 patients with a rare bleeding disorder are known to the eight Dutch centers that treat such patients. Approximately one third of these patients are homozygous; and around two thirds are heterozygous individuals.¹

All known homozygous and heterozygous patients with a rare bleeding disorder will be invited to participate.

Heterozygous prevalence in the Netherlands have not been evaluated, but can be calculated according to the Hardy-Weinberg principle² to be 93,000 to 99,000 persons, or 0.55% to 0.58% of the Dutch population (5.5 to 5.8 per 1,000 persons) for all rare bleeding disorders combined. Though the estimated number of heterozygous persons in the Netherlands is much higher than the number of persons known to one of the eight treating centers (~179 heterozygous patients³), we expect that the individuals with a known heterozygosity represent a subset with a more severe clinical presentation, who are therefore of interest to our research question.

Characteristics of the Dutch source population

The characteristics of the Dutch population (both homozygous and heterozygous) are largely unknown and are a part of this study. Numbers of known patients per rare bleeding disorder are presented in

[Table 3](#)

[Table 3.](#)

¹ A quick inventory in the Radboud university medical center learned that two thirds of patients were heterozygous individuals whereas one third were homozygous individuals. Based on an inventory of 63 medical files performed on July 8, 2016: 65% missing information, 24% heterozygosity, 11% homozygosity

² The Hardy-Weinberg proportion stipulates that for a single locus with two alleles denoted 'A' and 'a' with population frequencies p and q respectively, the expected genotype frequencies are p² for the AA homozygous individuals, q² for the aa homozygous individuals, and 2pq for the heterozygous individuals. The sum of these frequencies must be 1, thus p² + 2pq + q² = 1 and p + q=1.

Table 3 Prevalence of rare bleeding disorders in the Netherlands

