Deficiency	Estimated prevalence homozygosity in general population as described in the literature [1, 2]	Estimated prevalence homozygosity in the Dutch general population	Patients known at present in the Netherlands (homozygous/heterozygous/unknown)
Fibrinogen	1:1 million	17	28
II	1:2 million	9	9
V	1:1 million	17	22
V & VIII	1:1-2 million	9-17	4
VII	1:500,000	34	92
X	1:1 million	17	10
XI	1:1 million	17	88
XIII	1:1-2 million	9-17	16
PAI-1	Unknown	Unknown	39
Alpha-2-antiplasmin	Unknown	Unknown	29
	Total	129-145	337

Abbreviations: CI: confidence interval

\$ Based on a population figure of 17,024,133 (www.cbs.nl/nl-nl/visualisaties/bevolkingsteller)

* Based on a quick inventory of participating sites, which are all sites in the Netherlands licensed to treat rare bleeding disorders. Homozygosity or heterozygosity largely unknown

Willingness of patients to participate

We expect that a high proportion of patients with rare bleeding disorders are willing to participate in RBiN. Patients are aware of the rarity of their disorder and the lack of research. The Netherlands Hemophilia Society (Nederlandse Vereniging van Hemofilie Patiënten, NVHP) is a co-initiator of RBiN and a patient representative takes seat in the steering committee. Based on the response rate of the HiN studies we expect a (similar) response rate of 70% [51].

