7.2. Secondary objectives

- *Compare the clinical presentation, bleeding score, quality of life and laboratory parameters of individuals with a rare bleeding disorder (disorders of fibrinogen, FII, FV, FV & VIII, FVII, FX, FXI, FXIII and alpha-2-antiplasmin and PAI-1 deficiency) to those of individuals with haemophilia A or B (HiN study data will be shared)*
Descriptive statistics will be used. Group differences will be determined using the statistics as described in Statistical Analysis above.
- *Establish a firm base for a future Dutch registry for homozygous and known heterozygous individuals with rare bleeding disorders (disorders of fibrinogen, FII, FV, FV & FVIII, FVII, FX, FXI, d FXIII and alpha-2-antiplasmin and PAI-1 deficiency):*
 - *To develop a standard set of patient-reported, clinical and administrative data to be collected on a regular basis*

No statistics are involved in this objective.

- *Liaise with the pro-RBDD study, a similar study in Italy, to work towards a pan-European study linking phenotype to genotype in individuals with rare bleeding disorders*
No statistics are involved in this objective.
- *To assess if the NHA can distinguish mild clinical phenotypes in patients with similar factor activity levels*
We will calculate diagnostic accuracy comparing NHA to ISTH BAT.
- *To evaluate the usefulness of saliva coagulation biomarker tests in the management of patients with a rare bleeding disorder*
Descriptive statistics will be used. Regression analysis will be used to determine the association between saliva biomarker tests (dependent variable) and coagulation factor activity level as a continuous variable (independent variable), with adjustment for age at data collection, sex, etcetera.

- *To evaluate the use of WES in explaining differences in bleeding tendency.*
Descriptive statistics will be used.
- *To examine whether age-dependent laboratory changes in factor concentrations and fibrinolysis occur individuals with rare bleeding disorders? And if so, do they influence clinical phenotype?*
Descriptive statistics will be used. Regression analysis will be used to determine the association between age (dependent variable) and coagulation factor activity level as a continuous variable (independent variable), with adjustment for age at data collection, sex, etcetera.
- *To evaluate if patients with rare bleeding disorders are protected from arterial thrombosis*

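### Student's t-test and ordinary ANOVA are named for groups of very unequal size, with no provision for unequal variances; where sizes and SDs both differ, the stated 5% level is not held

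*Combined protocol and SAP*

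**What the plan says.** The general rule for continuous outcomes in section 7 is "Group differences will be determined using analysis of variance (ANOVA) or Student's t-test for continuous variables". The one stated exception is "Non-parametric tests will be used for results with non-normal distributions". The level is set by "Two-sided p-values smaller than 0.05 will be considered statistically significant", and multiplicity is waived: "Because of the explorative character of this study no correction for multiple testing will be applied". Nothing in section 7 deals with unequal variances or sets a minimum group size for testing.

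The rule is called on by name in section 7.2, for bleeding score, quality of life and laboratory values against haemophilia A or B: "Group differences will be determined using the statistics as described in Statistical Analysis above".

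The group sizes follow from section 5.1. It says "To date, 337 patients with a rare bleeding disorder are known to the eight Dutch centers that treat such patients", Table 3 splits these over ten disorders (4 for combined FV & VIII up to 92 for FVII), and on participation "we expect a (similar) response rate of 70" per cent.

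**The concern.** Student's t-test and ordinary ANOVA estimate one common variance, and the largest group dominates that estimate. If a small group is more variable than a large one, the standard error of the difference is too small: p-values are too small and confidence intervals too narrow. If the small group is less variable, the error runs the other way and real differences are missed. The plan's switch to rank tests responds to the shape of the distribution, not to unequal spread.

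Unequal spread is plausible here. Homozygous and heterozygous patients are mixed within disorders, and the background describes disorders that differ widely in bleeding severity. At stake is whether a p-value below 0.05, or a 95% interval, in the haemophilia comparison and in any contrast between disorders means what the plan says it means.

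**Working it through.** **Group sizes.** Known patients in Table 3 × 0.70:

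| Disorder | Known | Expected |
|---|---|---|
| FVII | 92 | 64.4 |
| FXI | 88 | 61.6 |
| PAI-1 | 39 | 27.3 |
| Alpha-2-antiplasmin | 29 | 20.3 |
| Fibrinogen | 28 | 19.6 |
| FV | 22 | 15.4 |
| FXIII | 16 | 11.2 |
| FX | 10 | 7.0 |
| FII | 9 | 6.3 |
| FV & VIII | 4 | 2.8 |
| Total | 337 | 235.9 |

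The known counts add up to the stated 337.

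**The plan's own figure.** With normal data, equal means and equal SDs, simulation gives 4.9-5.1% for Student's t and 5.0% for a ten-group ANOVA. The stated 5% is reproduced when the tests' own assumption holds.

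**Why it moves.** Let the smaller group have size n1 and SD r, and the larger group size n2 and SD 1.

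- True variance of the difference: V = r²/n1 + 1/n2.
- What the pooled test estimates on average: P = [((n1−1)r² + (n2−1)) / (n1+n2−2)] × (1/n1 + 1/n2).
- The nominal critical value then acts as if it were t × √(P/V).

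20 vs 64, r = 2: V = 4/20 + 1/64 = 0.2156. P = (19×4 + 63)/82 × (1/20 + 1/64) = 1.695 × 0.0656 = 0.1112. V/P = 1.94. The critical value 1.989 acts as 1.989/√1.94 = 1.43, a two-sided normal tail of about 15%. Simulation gives 15.8%.

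20 vs 64, r = 0.5: V = 0.25/20 + 1/64 = 0.0281. P = 67.75/82 × 0.0656 = 0.0542. V/P = 0.52, so 1.989 acts as 2.76, a tail of about 0.6%. Simulation gives 0.7%.

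62 vs 64 (FXI vs FVII), r = 2: V = 4/62 + 1/64 = 0.0801. P = 307/124 × (1/62 + 1/64) = 0.0786. V/P = 1.02, so almost nothing changes. Simulation gives 5.2%.

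**Simulated false-positive rates** (normal data, equal means; the SD ratios and the haemophilia group size are assumptions, since the documents give neither):

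| Comparison | Student, r = 0.5 | r = 1.5 | r = 2 | Welch |
|---|---|---|---|---|
| 11 vs 64 | 0.2% | 14% | 22% | about 5% |
| 20 vs 64 | 0.7% | 11% | 16% | about 5% |
| 62 vs 64 | 4.8% | 5.1% | 5.2% | about 5% |
| 236 vs 500 | 1.5% | 8.9% | 11.7% | about 5% |
| 236 vs 1000 | 0.4% | 12.5% | 18.4% | about 5% |

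Section 7.2 does not say whether the haemophilia comparison is pooled or made per disorder. If per disorder, 20 vs an assumed 1000 gives 18% at r = 1.5 and 31% at r = 2.

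**The fallback.** The rank test at 20 vs 64 gives 1.7%, 8.1% and 9.9% at r = 0.5, 1.5 and 2. This is closer to 5% but not a cure.

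**More than two groups.** With the seven groups of 10 or more, and FV and FXIII at 1.5 or 2 times the SD, ordinary ANOVA gives 11.6% and 19.8%. Welch's ANOVA gives 5.2-5.5% over the ratios tried. With all ten groups, Welch's ANOVA itself gives 9-10%, which is why a minimum group size is needed.

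**The case against.** The strongest reply has five parts.

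First, a reader might infer that the 5% level fails whenever spread differs. It does not: similar-sized groups stay at about 5%, and an SD ratio of 1.1 at 20 vs 64 gives only 6.2%. Unequal sizes and unequal SDs are both needed.

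Second, a reader might infer that the plan tests the ten disorders against each other. It names no such test; the only explicit use is the haemophilia comparison. Section 2 does speak of comparing the distinct disorders with haemophilia, so a per-disorder comparison there is a fair reading, but a ten-group ANOVA is inference.

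Third, the documents give no SDs. Statements about severity do not show that the small groups are the more variable ones, and they may be less so. The size of the error is therefore conditional, though it is wrong in either direction.

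Fourth, a reader might infer that the primary results are compromised. The primary objectives rest on description and regression, the arterial thrombosis objective has its own Wilcoxon tests, and the study is declared exploratory. That limits the consequence. It does not remove the point, because waiving multiplicity correction concerns the number of tests, not whether each one holds its own 0.05.

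Fifth, Welch is not free. With equal SDs and Student's power set at 80%, Welch has about 66% at 6 vs 64, 75% at 11 vs 64 and 78% at 20 vs 64. With identical strongly skewed distributions (exponential and lognormal), Welch rejects in 11-14% at 6 vs 64 and 8-10% at 11 vs 64, where Student stays near 5%. This stands, and it is the reason to leave groups below about 10 untested and to keep the rank-test rule for skewed outcomes.

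**Conclusion.** The point holds in a limited form. Section 7 names pooled-variance tests, has no rule for unequal variances, and carries them into a comparison in which group sizes may differ severalfold. If the smaller group's SD is 1.5 to 2 times the larger group's, the nominal 5% becomes 11-16% at 20 vs 64, 14-22% at 11 vs 64, and 9-18% for all 236 participants against an assumed 500-1000 haemophilia patients. At half the SD it falls below 1% in the two disorder contrasts and to 0.4-1.5% in the pooled comparison. These figures rest on normal data, assumed SD ratios, an assumed haemophilia group size and the 70% response. Comparisons between groups of similar size are sound as planned. This is an inexpensive improvement to exploratory, mainly secondary comparisons, not a defect in the primary analyses.

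**What to change.** In section 7, replace Student's t-test with Welch's t-test and ordinary ANOVA with Welch's ANOVA, and take confidence intervals for differences from the same method. State in section 7.2 that this applies to the haemophilia comparison. Add that groups of fewer than about 10 participants (expected: FV & VIII about 3, FII about 6, FX about 7) are reported descriptively, without a formal test. Keep the non-parametric rule for clearly skewed outcomes.

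The cost is two or three sentences and no new data. If the SDs are in fact equal, power of 80% falls to about 75% at 11 vs 64 and about 78% at 20 vs 64. The three smallest disorders get no p-value. In groups of about 11 with strongly skewed data, Welch's error rate is still raised to about 8-10%, so the rank-test rule should take over there.

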FXI deficiency can be inherited autosomal recessive and autosomal dominant[33]. It is the mildest of the rare bleeding disorders, with bruising, epistaxis and menorrhagia as the most common manifestations [5, 14]. The correlation between coagulation factor activity and clinical bleeding is poor [19]. This may (in part) be explained by the coexistence of other coagulation disorders. In some patients with severe FXI deficiency a combined FXI and von Willebrand disease has been reported, leading to a more severe bleeding tendency [16]. Excessive bleeding has also been reported in heterozygous individuals. A single study from the United Kingdom showed that 48% of heterozygous individuals had a bleeding tendency, [34]. Comparison of histories between partially deficient and non-deficient individuals demonstrated a higher prevalence of menstrual problems (41% vs. 18%), an increase in significant bruising (38% vs. 14%), an increased likelihood of excessive bleeding after dental extractions (51% vs. 9%), and an increased number of blood transfusions after interventions (56% vs. 0%). Bleeding in heterozygous individuals has also been described to be related to genetically compound disease, other factor deficiencies or defects, or platelet dysfunction in some cases [12-18].

FXIII deficiency

FXIII deficiency is an autosomal recessive disorder. This deficiency has serious clinical consequences. Of 112 cases reported in the literature from 1978 23 individuals (21%) had died of bleeding, and notably 22 of these were relatives of established cases, for whom the diagnosis was highly likely but could not be proven [35]. Umbilical cord bleeding was seen in

73-80% of cases and may be delayed up to 19 days after birth; surgical bleeding in 84%; superficial bruising in 58-60%; subcutaneous haematomas in 55-58%; intracranial bleeding in 25-30%; mouth and gum bleeding 30-48%; muscle bleeding 27%; and joint bleeding in 24-55% of reported cases [35, 36]. Habitual abortions (50% of women) and menorrhagia (35% of women) are also frequent. Women with a complete deficiency are unable to carry a pregnancy to term [36, 37]. Impaired wound healing is another symptom patients may experience [37]. It is currently not clear if people with a heterozygous factor XIII deficiency have an increased bleeding risk[38].

Alpha-2-antiplasmin deficiency

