1.5. Genetics

In general, mutations in genes that encode for the corresponding coagulation factor are the cause of the bleeding disorder, and mutations are almost always unique to single kindred (Table 2). The combined deficiency of FV & FVIII is caused by mutations in genes encoding for proteins involved in intracellular transport [41]. Deficiencies in the vitamin K dependent coagulation proteins (FII, FVII, FIX and FX) can be caused by mutations in genes encoding enzymes involved in post-translational modification and in vitamin K metabolism [42].

In approximately 10% to 20% of patients, no putative mutation is found with conventional genetic techniques that scan the 'usual suspect' genes. Cases where no putative mutation has been found may be due to defects in non-coding regions or in genes coding for regulators of intracellular transport and posttranslational modifications of coagulation factors.

Table 2 General genetic features of the rare bleeding disorders [10, 23]

Disorder factor	Gene on chromosome
Fibrinogen	4
II	11
V	1
V & VIII	18

VII	13
X	13
XI	4
XIII	A subunit: 6 B subunit: 1
PAI-1	7
Alpha-2-antiplasmin	17

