5.3. Exclusion criteria

A potential subject who meets any of the following criteria will be excluded from participation in this study:

- No informed consent given;
- Residency outside of the Netherlands

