7.1. Primary objectives

- *Describe the epidemiology, clinical presentation, bleeding score, bleeding episodes, quality of life, laboratory parameters, genetics and treatment of homozygous and known heterozygous individuals (of all ages) with rare bleeding disorders (disorders of fibrinogen, FII, FV, FV & VIII, FVII, FX, FXI, FXIII and alpha-2-antiplasmin and PAI-1 deficiency) in the Netherlands;*

We will use descriptive statistics using means, SD and medians. Interquartile ranges will be used when appropriate. Prevalence will be reported with 95% confidence intervals.

- *Examine the relationship between clinical and laboratory presentation (clinical and laboratory phenotype), and between phenotypes and genetics (genotype);*

Descriptive statistics will be used. Regression analysis will be used to determine the association between coagulation factor activity level (dependent variable) and clinical

bleeding severity as a continuous variable (independent variable), with adjustment for age at data collection, sex, etcetera.

- *Examine the relationship between quality of life, phenotype and genotype;*
Descriptive statistics will be used. Regression analysis will be used to determine the association between quality of life (dependent variable) and clinical bleeding severity or coagulation factor activity level as a continuous variable (independent variable), with adjustment for age at data collection, sex, etcetera.
- *Validate the established factor activity levels for patients to remain without symptoms.*
Descriptive statistics will be used.

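### Relatives who enrol would be analysed as independent patients, so p-values and CIs for factors shared within a family would be too optimistic

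*Combined protocol and SAP*

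**What the plan says.** **Recruitment.** Section 5.1: "All known homozygous and heterozygous patients with a rare bleeding disorder will be invited to participate". Section 5.3 has two exclusions, lack of consent and "Residency outside of the Netherlands", so relatives may enter together. Section 8.4 puts minors at about a third of known patients, and they are recruited alongside adults.

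**Inheritance.** Section 1.5 says that "mutations are almost always unique to single kindred". Section 1.2 describes most of the disorders as recessive, but gives hypofibrinogenemia as dominant and dysfibrinogenemia as either. For one of the two largest groups it says "FXI deficiency can be inherited autosomal recessive and autosomal dominant".

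**Analysis.** Section 7: "Group differences will be determined using analysis of variance (ANOVA) or" a t-test when the outcome is continuous, and Fisher's exact test when it is categorical. Non-parametric tests replace these for non-normal data, and summaries carry 95% CIs. The threshold is "Two-sided p-values smaller than 0.05 will be considered statistically significant", with no multiplicity correction because the study is exploratory. The regressions in sections 7.1 and 7.2 are specified "with adjustment for age at data collection, sex, etcetera". For arterial thrombosis, section 7.2 adds chi-squared and Wilcoxon tests. Nowhere in section 7 is there a family term, random effect, GEE, cluster-robust variance or one-per-family analysis.

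**Data.** Table 4 (section 6.1) lists no family or pedigree field. Under section 9.1, subject codes combine a centre code and a serial number, and each centre holds its own key.

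**The concern.** If almost every mutation belongs to one kindred, genotype is close to a family label. Factor level and bleeding tendency plausibly resemble each other among relatives. A second member of a family then adds less information than an unrelated patient, but the planned methods count both in full.

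The relation between phenotype and genotype is a primary objective, and so are the regressions linking factor level, bleeding severity and quality of life. Standard errors that are too small would produce false leads in a field where few other cohorts exist to correct them. The gap may also be hard to close afterwards: the central analysts cannot link relatives from the subject codes, least of all across centres. Exome sequencing is only a partial substitute, since it is not done in the younger children.

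**Working it through.** **What can be reproduced.** The plan states no sample size, power, number of families or intra-family correlation, so there is no design figure to reproduce. The base does check: the counts in Table 3 sum to 28+9+22+4+92+10+88+16+39+29 = 337. The 70% response expected in section 5.1 gives 0.70 × 337 = 235.9, about 236 patients.

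**Inputs that must be assumed.** *m* is the number of enrolled patients per family (size-weighted mean when families differ in size), taken from 1.25 to 3. ICC is the intra-family correlation of the outcome, taken from 0.2 to 0.8. Neither is in the documents.

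**Formulas, for a factor shared by the whole family.**
- Design effect: DEFF = 1 + (m − 1) × ICC
- True two-sided error of a nominal 5% test: 2 × [1 − Φ(1.96/√DEFF)]
- Factor by which the CI should be wider: √DEFF
- Effective sample size: 236/DEFF

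Example, m = 2 and ICC = 0.5: DEFF = 1.5; 1.96/√1.5 = 1.60; true error 11.0%; CI 1.22 times wider; effective N = 157.

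| m | ICC 0.2 | ICC 0.5 | ICC 0.8 |
|---|---|---|---|
| 1 (no relatives) | 5.0% | 5.0% | 5.0% |
| 1.25 | 5.6% | 6.5% | 7.4% |
| 1.5 | 6.2% | 8.0% | 9.8% |
| 2 | 7.4% | 11.0% | 14.4% |
| 3 | 9.8% | 16.6% | 22.4% |

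From the mildest to the most severe cell with relatives, DEFF runs from 1.05 to 2.6. Coverage of a nominal 95% CI falls from 94% to 78%, the correct CI is 1.02 to 1.61 times wider, and effective N goes from 225 to 91.

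**Check by simulation.** Ordinary t-tests were simulated on about 64 patients (70% of the 92 known FVII patients), with 8,000 runs per setting and families of unequal size:

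| Plain mean family size | Factor shared by family (ICC 0.2 / 0.5 / 0.8) | Factor independent of family | Factor contrasted within family (ICC 0.2 / 0.5 / 0.8) |
|---|---|---|---|
| 1.0 | 4.8 / 5.0 / 4.9% | 4.8–5.1% | 5.1 / 4.9 / 5.4% |
| 1.4 (size-weighted 1.71) | 6.4 / 9.3 / 11.1% | 4.9–5.2% | 4.1 / 3.0 / 1.4% |
| 2.0 (size-weighted 2.5) | 8.3 / 13.5 / 18.8% | 4.7–5.3% | 3.7 / 1.7 / 0.2% |

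The formula agrees: for size-weighted m = 2.5 and ICC = 0.5, DEFF = 1.75 and the error is 13.8%, against 13.5% simulated.

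**Regressions.** When predictor and outcome both cluster, the approximate design effect for the slope is 1 + (m − 1) × ICC_x × ICC_y. With both correlations at 0.5, m = 2 gives 1 + 0.25 = 1.25 and 8.0%; m = 3 gives 1 + 2 × 0.25 = 1.5 and 11.0%. The inflation is real but smaller than for a fully shared factor.

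**The case against.** **Enrolment of relatives is an inference.** No count of families is given. Section 5.1 points partly the other way: about 179 heterozygotes are known against 93,000-99,000 expected, and the known ones are thought to be more severely affected. That suggests detection through symptoms more than family tracing. A 70% response thins families further. This stands, and it is why the range must start near 5%. Dominant forms and the joint recruitment of minors and adults still make some relatives likely.

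**The direction is not uniform.** A reader might infer that every genotype or phenotype comparison is anti-conservative. The documents do not support that. Most of the disorders are described as recessive, so homozygous versus heterozygous relatives is a natural contrast, and there the planned tests are conservative and lose power.

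**Genotype is mainly described, not tested.** Sections 7.1 and 7.2 plan descriptive statistics for genotype and for exome sequencing. No pooled genotype t-test on 236 patients is specified. This stands. The problem reaches genotype through the general group tests and CIs of section 7, and reaches the named regressions directly.

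**The known patients may be the target population.** If inference stops at the 337, sampling 70% gives a finite-population factor of about √0.30 = 0.55, which can offset the clustering in descriptive CIs. This holds for describing that group, but not for relationships meant to apply beyond it.

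**The study is exploratory.** That explains the absence of multiplicity correction. It does not make a standard error correct, and uncorrected testing at 0.05 leaves no margin.

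**A family link may be recorded elsewhere.** The questionnaires are separate documents and the case report form is not shown, so one can say only that Table 4 lists none. The open-ended covariate list could hide a family term, but does not specify one, and a covariate would not repair the exact and rank tests.

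**Conclusion.** The omission is real and worth correcting before data collection closes. As written, the plan understates uncertainty for factors shared within a family, and for associations between variables that both cluster in families, to the extent that relatives enrol. It overstates uncertainty for within-family contrasts and is about right for factors unrelated to family.

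The size cannot be fixed from the documents. Over ICC 0.2 to 0.8, a nominal 5% test of a family-shared factor has a true error of 5.6-9.8% at a size-weighted mean of 1.25-1.5 patients per family, 7-14% at 2 and 10-22% at 3. If nearly all patients are singletons, it is 5%. A reader might take the upper end as the expected case, but that needs an average of two or three enrolled members per family, which nothing in the documents establishes. The consequence is misjudged precision and extra false leads in an exploratory study, not a wrong confirmatory decision.

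**What to change.** - **Record** a family identifier, valid across centres, and index-patient or relative status on the case report form. If the questionnaires or the form already hold this, say so in the protocol.
- **Report** the number of families as well as patients for each disorder.
- **Regressions and pooled group comparisons:** use a family random effect, GEE or cluster-robust variance where there are enough families.
- **Exact and rank tests, and small disorder groups:** use a family-level permutation test or a sensitivity analysis with one patient per family. Cluster-robust errors are unreliable with few clusters, and Table 3 lists only 4, 9, 10 and 16 known patients for four disorders before non-response.
- **Within-family contrasts,** such as zygosity among relatives: use the same family-aware model, which here recovers power.

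The cost is two data fields, a standard software option and, for family-shared factors, somewhat wider CIs. If few relatives enrol, the results will hardly change. The family link would also serve the future registry named in the secondary objectives.
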